5.4.2.2 Secondary Efficacy Analyses

The secondary efficacy endpoints include BOR over the treatment period (except for Cohort 2A), ORR (except for Cohort 2A), DCR, and CBR, as well as DOR (measurable disease only). PFS and TTP are defined in SAP [Section 5.1](#) and will be performed for subjects in the Full Analysis and Per Protocol Analysis Sets.

Subjects who do not have a tumor response assessment for any reason will be considered nonresponders and will be included in the denominator when calculating the response rate. The count and percentage for ORR will be summarized by dose level for Cohorts 1 and 3A and by cohort for Cohorts 2B and 3B. ORR and corresponding 95% CI based on the exact binomial distribution will be estimated for all corresponding treatment cohorts.

The count and percentage for both the DCR and CBR will be summarized for each treatment cohort, along with the exact 95% CI for.

The median and quartiles of DOR will be estimated by the Kaplan-Meier (KM) method ([Kaplan and Meier, 1958](#)), and the 95% CI estimated with a generalized Brookmeyer and Crowley method ([Brookmeyer and Crowley, 1982](#)).

For PFS, if a subject has not experienced PD or death, then the subject's data will be censored on the date of the last adequate radiologic assessment.

TTP will be calculated using data from all subjects in the Full Analysis Set. The calculation for TTP does not classify deaths as events.

The PFS censoring rules in this SAP and definition of progression date follow the [Food and Drug Administration \(FDA\), Guidance for Industry Clinical Trial Endpoints for the Approval of Cancer Drugs and Biologics \(2007\)](#) (See SAP Table 3). The PFS censoring rules are referenced in SAP Table 3 and TTP censoring rules are referenced in SAP Table 4.

Table 3 Censoring Rules for Analysis of Progression-Free Survival

No	Situation	Date of Progression or Censoring	Outcome
1	No baseline tumor assessments	Date of first dose	Censored
2	No postbaseline tumor assessments	Date of first dose	Censored
3	Progression documented between scheduled visits	Date of first radiologic PD assessment	Progressed
4	More than 1 NE tumor timepoint assessment	Date of last adequate radiologic assessment before NE tumor assessments	Censored
5	No progression at time of data cutoff	Date of last adequate radiologic assessment	Censored
6	New anticancer treatment started	Date of last adequate radiologic assessment prior to or on date of new anticancer treatment	Censored
7	Death before first tumor assessment	Date of death	Progressed
8	Death between adequate assessment visits*	Date of death	Progressed
9	Death or progression after more than one missed visit/tumor assessment**	Date of last adequate radiologic assessment before missed tumor assessments	Censored
10	Treatment discontinuation for reasons other than PD	Date of last radiologic assessment before treatment discontinuation	Censored

CR = complete response, NE = not evaluable, PD = progressive disease, PR = partial response, q6w = every 6 weeks, q8w = every 8 weeks, SD =stable disease.

* Adequate tumor assessment is radiologic assessment at regular interval as defined in the protocol.

** More than 1 missed visit/adequate tumor assessment is defined as having either 1 of the following 2 durations being longer than 18 weeks – 1 day, which is 125 days ($= ((8+1) \times 2 \times 7) - 1$) for subjects on the q8w tumor assessment schedule in Cohorts 1, 2A and 2B; while 14 weeks – 1 day, which is 97

days (= ((6+1) x 2 x 7) – 1) for subjects on the q6w tumor assessment schedule in Cohorts 3A and 3B:

- a. Duration between 2 consecutive tumor assessments
- b. Duration between the last adequate tumor assessment and death or PD

The priority of the censoring rules is as follows:

1. If the subject had PD or death, the following sequence will be applied:

- If a subject did not have a baseline or postbaseline tumor assessment (Nos. 1 and 2), the subject will be censored on the date of first dose. However, if the subject died within 125 days in Cohorts 1, 2A and 2B or 97 days in Cohorts 3A and 3B following the first dose and did not receive a new anticancer treatment, it will be counted as PFS event at the date of death. If a subject had new anticancer treatment before PD or death (No. 6), the subject will be censored on the date of the last adequate tumor assessment prior to or on the date of new anticancer treatment. If PD is reported after the drug discontinuation visit, the subject will be censored at the date of last radiologic assessment before drug discontinuation except when PD happened at the same visit as drug discontinuation (No. 10). If PD happened within 4 weeks of drug discontinuation (Week 16 for Cohort 2 and Week 18 for Cohorts 3A and 3B), it will be considered PD at drug discontinuation visit and counted as PFS event.
- If a subject missed 2 or more tumor assessments before PD or death (No. 9), the subject will be censored on the date of the last adequate tumor assessment before PD or death. Note that if a subject is censored by both this criterion and the anticancer treatment criterion, the earliest censoring date will be used.
- Otherwise, if a subject had an event (No. 3, No. 7, or No. 8), the earliest event date will be used.

2. If a subject did not have PD or death, the censoring date will be the earliest censoring date if the subject met multiple censoring criteria (No. 1, No. 2, No. 4, No. 5, No. 6, No. 9).

Table 4 Censoring Rules for Analysis of Time to Progression

No	Situation	Date of Progression or Censoring	Outcome
1	No baseline tumor assessments	Date of first dose	Censored
2	No postbaseline tumor assessments	Date of first dose	Censored
3	Progression documented between scheduled visits	Date of first radiologic PD assessment	Progressed
4	More than 1 NE tumor timepoint assessment	Date of last adequate radiologic assessment before NE tumor assessments	Censored
5	No progression at time of data cutoff	Date of last adequate radiologic assessment	Censored
6	New anticancer treatment started	Date of last adequate radiologic assessment prior to or on date of new anticancer treatment	Censored
7	Death before first tumor assessment	Date of death	Censored
8	Death between adequate assessment visits*	Date of death	Censored
9	Death or progression after more than one missed visit/tumor assessment**	Date of last adequate radiologic assessment before missed tumor assessments	Censored
10	Treatment discontinuation for reasons other than PD	Date of last radiologic assessment before treatment discontinuation	Censored

CR = complete response, NE = not evaluable, PD = progressive disease, PR = partial response, q6w = every 6 weeks, q8w = every 8 weeks, SD =stable disease.

* Adequate tumor assessment is radiologic assessment at regular interval as defined in the protocol.
** More than 1 missed visit/adequate tumor assessment is defined as having either 1 of the following 2 durations being longer than 18 weeks – 1 day, which is 125 days ($= ((8+1) \times 2 \times 7) - 1$) for subjects on the q8w schedule for tumor assessment in Cohorts 1, 2A, and 2B; while 14 weeks – 1 day, which is 97 days ($= ((6+1) \times 2 \times 7) - 1$) for subjects on the q6w schedule for tumor assessment in Cohorts 3A and 3B:

- a. Duration between two consecutive tumor assessments
- b. Duration between the last adequate tumor assessment and PD

The priority of the censoring rules is as follows:

1. If the subject had PD, the following sequence will be applied:
 - If a subject did not have a baseline or postbaseline tumor assessment (Nos. 1 and 2), the subject will be censored on the date of first dose. If a subject had new anticancer treatment before PD (No. 6), the subject will be censored on the date of the last adequate tumor assessment prior to or on the date of new anticancer treatment. If PD is reported after the drug discontinuation visit, the subject will be censored at the date of last radiologic assessment before drug discontinuation except when PD happened at the same visit as drug discontinuation (No. 8). If PD happened within 4 weeks of drug discontinuation (Week 16 for Cohort 2 and Week 18 for Cohorts 3A and 3B), it will be censored at drug discontinuation visit.
 - If a subject died before first tumor assessment (No. 7) or died between adequate assessment visits (No. 8), the subject will be censored on the date of death.
 - If a subject missed 2 or more tumor assessments before PD or death (No. 9), the subject will be censored on the date of the last adequate tumor assessment before PD or death. Note that if a subject is censored by both this criterion and the anticancer treatment criterion, the earliest censoring date will be used.
 - Otherwise, if a subject had an event (No. 3), the earliest event date will be used.
2. If a subject did not have PD, the censoring date will be the earliest censoring date if the subject met multiple censoring criteria (No. 1, No. 2, No. 4, No. 5, No. 6, No 9).

The distribution of PFS and TTP will be estimated using the KM method. Median, Q1 and Q2 times to PFS, TTP, and the 95% CIs will be provided for each treatment cohort (estimated with the Brookmeyer and Crowley method). Four-month and 12-month PFS and TTP rates will be estimated using the KM method and corresponding 80 and 95% CIs will be provided (estimated with the Greenwood formula using the log-log transformation [Greenwood, 1926; Kalbfleisch and Prentice, 2002]) when an adequate number of at-risk subjects at those time points warrant the estimate. Follow-up time for PFS and follow-up time for progression-free duration will be presented for PFS and TTP, respectively (estimated using the KM method with median, Q1, and Q2 times). The 95% CIs will be estimated with the Brookmeyer and Crowley method. Estimates for both PFS and TTP follow-up times are calculated in the same way as the KM estimates of PFS and TTP, but with the meaning of ‘censor’ and ‘event’ status indicator reversed.

The secondary efficacy analyses for Cohort 3B will be based on the lenvatinib-naïve subjects in the Full Analysis Set, while subjects enrolled from Cohorts 1 and 2B will be summarized as appropriate.

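### In the SAP's PFS and TTP censoring rules, a long scan gap at any earlier time triggers row 9 and cancels a progression later documented on schedule; separately, table and priority text give different censoring dates

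*SAP*

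**What the plan says.** All of this is in SAP 5.4.2.2, Secondary Efficacy Analyses.

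- **Trigger.** The double-asterisk footnote to Table 3 reads "More than 1 missed visit/adequate tumor assessment is defined as having either 1 of the following 2 durations being longer than 18 weeks" less one day, "which is 125 days" on the 8-weekly schedule, and "14 weeks – 1 day, which is 97" days on the 6-weekly schedule. Item (a) is "Duration between 2 consecutive tumor assessments". Item (b) is "Duration between the last adequate tumor assessment and death or PD". Table 4 (TTP) repeats (a) as "Duration between two consecutive tumor assessments"; its (b) covers PD only.
- **Censoring date in the tables.** Row 9: "Date of last adequate radiologic assessment before missed tumor assessments".
- **Censoring date in the priority text for No. 9, PFS and TTP.** "the subject will be censored on the date of the last adequate tumor assessment before PD or death".
- **Order.** In step 1 of both priority lists No. 9 comes before the step that counts events, and that step is reached only if No. 9 did not apply.
- **Step 2.** For subjects without PD or death (PFS) or without PD (TTP), the earliest of several censoring dates is used, and No. 9 is among the criteria listed.
- **Statement ahead of Table 3.** A subject with neither PD nor death is censored for PFS at the last adequate radiologic assessment. Row 5 says the same for subjects without progression at data cutoff.

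**The concern.** A missed-assessment rule exists for events whose timing is obscured by a gap. Item (b) describes that case. Item (a) does not: it is met by any long gap in the subject's history, even when adequate scans without PD followed and the PD was then found at the next scheduled scan. Such a PD is dated as well as any other, yet it is not counted.

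There are two further defects. Once scanning has resumed, the table and the priority text name different censoring dates, so two programmers can follow the SAP and get different curves. And a subject who never progressed can be censored back at an old gap, losing later follow-up that was verified as progression-free.

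At stake are the Kaplan-Meier medians and the 4- and 12-month PFS and TTP rates, and the reverse Kaplan-Meier follow-up times, which use the same status flags. The expansion cohorts have about 12 (2A), 15 to 30 (2B) and 18 lenvatinib-naïve (3B) subjects, so one event can be visible.

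**Working it through.** **1. Thresholds.** The SAP's formulas reproduce: ((8+1) × 2 × 7) − 1 = 125 days and ((6+1) × 2 × 7) − 1 = 97 days.

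**2. What sets off (a).** Scheduled intervals are 56 days (8-weekly) and 42 days (6-weekly).
- One missed scan: 2 × 56 = 112 and 2 × 42 = 84, neither over the threshold.
- Two missed: 3 × 56 = 168 > 125 and 3 × 42 = 126 > 97.
- One missed and the next 14 days late: 112 + 14 = 126 > 125 and 84 + 14 = 98 > 97.

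**3. Early gap, scans resume, PD on schedule.**

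| | 8-weekly | 6-weekly |
|---|---|---|
| Scans without PD (days) | 56, 112, 280, 336 | 42, 84, 210, 252 |
| PD (day) | 392 | 294 |
| Gap (a) | 280 − 112 = 168 > 125 | 210 − 84 = 126 > 97 |
| Gap (b) | 392 − 336 = 56, not met | 294 − 252 = 42, not met |
| Table date | 112 | 84 |
| Priority-text date | 336 | 252 |
| Difference | 224 days (7.4 months) | 168 days (5.5 months) |

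Months use the SAP's 30.4375 days. The PD is lost under either date. Item (a) and the order of the rules cause that; the date conflict decides only where the subject is censored.

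**4. Gap that ends at the event.** Scans at 56 and 112, PD at 280: (b) is 168 > 125 and both texts give day 112. Scans at 42 and 84, PD at 210: (b) is 126 > 97 and both give day 84. So table and text agree here and part only when an adequate scan lies between the gap and the event.

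**5. Event-free subject, PFS step 2.** Scans at 56, 112, 280 and 336, no PD or death at cutoff. Row 9 gives day 112 and row 5 gives day 336; the earliest is day 112. The statement ahead of Table 3 gives day 336. Verified time dropped: 336 − 112 = 224 days.

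**6. Size in one assumed cohort.** Take 27 subjects with PD at day 56 (8), 112 (6), 168 (4), 224 (3), 392 (3) and 448 (3). Let g of the three day-392 progressors have the gap in step 3.
- 4 months (day 121.75): 13/27 = 48.1% for every g.
- 12 months (day 365.25), text date: 13/27 × 9/13 × 6/9 = 6/27 = 22.2%, the same as when the PDs are counted, since day 392 is past 12 months.
- 12 months, table date: the product reduces to 13/27 × (6 − g)/(13 − g). g = 1: 13/27 × 5/12 = 20.1%. g = 2: 13/27 × 4/11 = 17.5%. g = 3: 13/27 × 3/10 = 14.4%.

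**7. Size by simulation.** The comparison is (b) alone against (a) or (b). PFS is exponential, each affected subject has one two-scan gap, and gap rates are assumed.
- 12 subjects, 60% PFS at 12 months, 520 days of follow-up, gaps in 20%, table date: mean events fall from 5.7 to about 5.2. The 12-month rate in a single trial moves by about −11 to +5 points (5th to 95th percentile).
- Same cohort, gaps in 10%, follow-up uniform on 168 to 900 days: events fall from 5.7 to 5.5. The shift is −6 to 0 points under the table date; under the text date the rate is unchanged in about 96% of trials.
- 27 subjects at the Cohort 2B design rates (PFS-4 of 25% or 45%), gaps in 5 to 10%: mean shift under 1 point with either date.

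**The case against.** **A narrower reading.** Row 9 describes a PD or death that follows missed assessments, and the priority text's date makes most sense when the gap runs straight into the event. Read so, table and text agree and no on-schedule PD is lost. But the footnote says either duration suffices and does not tie (a) to the event. If (a) meant only the interval ending at PD, (b) would already cover it, and No. 9 could never operate in PFS step 2, where there is no event. The narrow reading may be what was intended; it is not what is written.

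**The event-free case is contradictory, not settled.** The statement ahead of Table 3 and row 9's own description both point away from applying No. 9 to these subjects. This stands: the point is that step 2 conflicts with them, not that the follow-up will certainly be lost.

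**Rarity.** The protocol keeps the scan schedule irrespective of treatment delays (Section 9.5.1.3), and the pattern needs long follow-up. With one scan before a two-scan gap, a subject must still be progression-free at about Week 32. With exponential PFS at the design rates that is 27 × 0.25^(224/121.75) ≈ 2 to 27 × 0.45^(224/121.75) ≈ 6 subjects in Cohort 2B. This stands and limits the size.

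**Possible deliberate choice.** The SAP says its PFS rules follow a cited regulatory guidance. That source is not available here, so whether (a) was a deliberate conservative choice cannot be judged. It would not resolve the two dates or step 2.

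**Stronger readings the documents do not support.** A reader might infer that the primary result is at risk. It is not: PFS-4 is a binomial rate with its own evaluability rules (SAP 5.4.2.1) that do not use row 9, and Cohort 2A's primary endpoints are ORR and BOR. A reader might also infer that the date conflict is what discards the PD; step 3 shows otherwise.

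**Conclusion.** The concern holds for the secondary Kaplan-Meier PFS and TTP analyses. As written, item (a) together with the rule order turns a well-dated progression into a censored observation. Table and priority text then disagree on the date whenever adequate scans resumed before the event, and PFS step 2 contradicts the SAP's own statement for subjects without PD or death.

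The effect falls mainly on later time points and is small at 4 months. With no such gaps nothing changes. The documents give no gap frequency, so the figures in steps 6 and 7 are illustrations under assumed PFS distributions, follow-up and gap rates, not forecasts for this trial. It is worth correcting because two analysts following the SAP could report different curves from the same data.

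**What to change.** In SAP 5.4.2.2:

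1. In the footnotes to Tables 3 and 4, delete item (a) and keep (b), so row 9 applies only to the gap that directly precedes the event: PD or death for PFS, PD for TTP. With this change the PDs at days 392 and 294 in step 3 count as events, and the subjects in step 4 are still censored at days 112 and 84.
2. State one date in tables and priority text: the last adequate assessment before that gap.
3. Remove No. 9 from PFS step 2, so subjects without PD or death are censored at the last adequate assessment, as the text ahead of Table 3 already says.
4. In TTP step 2, drop the any-gap trigger for subjects without PD, but do not simply censor all of them at the last adequate scan. Table 4 rows 7 and 8 censor deaths at the date of death, row 9 also names deaths after missed assessments, and Table 4's (b) covers PD only. State explicitly how a death without PD is censored so that the list and rows 7 to 9 agree.
5. If the any-gap rule is wanted, keep it as a labelled sensitivity analysis with one stated date.

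The cost is SAP wording and a small programming change. No new data are needed.

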9.1.3 Post-treatment (All Cohorts)

The Post-treatment Follow-up begins when the subject discontinues treatment. After subject discontinues treatment, an Off-Treatment Visit and the procedures noted in the Schedule of Assessments Tables ([Table 7](#), [Table 8](#), and [Table 9](#)) should be completed within 30 days after the last dose of drug. Subjects will be followed for survival every 3 months until death or for 1 year, whichever occurs first, unless the study is terminated or the subject discontinues due to withdrawal of consent or is lost to follow-up (see [Section 9.3.3](#)).

Subjects who discontinue treatment without disease progression will have tumor assessments performed every 6 or 8 weeks (per the appropriate tumor assessment schedule) for up to 1 year, or sooner if clinically indicated, for documented disease progression or until another anticancer therapy is initiated whichever occurs first. After data cutoff, tumor assessments may be performed as clinically indicated using the institutional guidelines, following the prevailing local standard of care.

As required by some regulatory agencies, the following estimates are provided:

- The study will begin in December 2014 and will end on or before December 2017.
- The maximum estimated period for the study is anticipated to be approximately 36 months. However, subjects will continue to receive study treatment as long as they demonstrate clinical benefit. Subjects benefiting from study treatment in the opinion of the investigator will continue to receive treatment until disease progression, intolerable toxicity, subject noncompliance with safety or efficacy assessments, initiation of another anticancer therapy, voluntary discontinuation by the subject at any time, or study termination by the sponsor, whichever occurs first.

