9.4.8.2 Prohibited Concomitant Therapies and Drugs

Subjects should not receive other antitumor therapies while on study. If subjects receive additional antitumor therapies, such as chemotherapy, hormone therapy with well-known direct antitumor activity against the subject's malignancy, palliative radiotherapy (other than as described below), or immunotherapy, this will be judged to represent evidence of disease progression, and study medication will be discontinued. These subjects should complete all off-treatment assessments and continue to be followed for survival in the Post-treatment Follow-Up.

Prophylactic use of G-CSF is not permitted during this study for Cohorts 1, 2A, and 2B. G-CSF is recommended for Cohorts 3A and 3B to mitigate the toxicity of ifosfamide and etoposide).

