5.4.2.1 Primary Efficacy Analyses

COHORT 2A: DTC

The primary efficacy endpoint is ORR for subjects with measurable disease and BOR for all subjects. Tumor response will be based on RECIST 1.1 and assessed every 8 weeks. The analysis will be descriptively performed on the Full Analysis Set.

COHORT 2B: SINGLE-AGENT EXPANSION

The primary efficacy endpoint is the PFS-4 rate based on RECIST 1.1. This is the proportion of subjects free of progression at 4 months. The PFS-4 rate will be estimated using the binomial proportion and the corresponding 80% and 95% exact binomial distribution CIs ([Clopper and Pearson, 1934](#)) will also be provided. The PFS-4 rate will also be tested using a null hypothesis that the PFS-4 rate is $\leq 25\%$ tested against the alternative hypothesis of a PFS-4 rate $\geq 45\%$, using the 1-sample exact test of a single proportion, at the 1-sided 0.1 level. These analyses will be performed on the lenvatinib-naïve subjects in the Full Analysis Set and the Per Protocol Analysis Set.

The PFS-4 rate will be calculated using PFS-4 evaluable subjects. These are defined as follows.

PFS-4 evaluable subjects:

- includes subjects who were treated with study medication at least 16 weeks;
- includes subjects who died or radiologically progressed within 16 weeks after the first administration of study medication. These subjects are not considered free of progression at 4 months;
- includes subjects who received anticancer treatment within 16 weeks after the first administration of study medication. These subjects are not considered free of progression at 4 months;
- excludes those who discontinue the study due to AE or reasons other than disease progression, death, or receiving anticancer treatment within 16 weeks after the first administration of study medication;
- excludes subjects administered any study medication with no baseline or no postbaseline tumor assessments.

COHORT 3B: OSTEOSARCOMA COMBINATION EXPANSION

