The primary efficacy endpoint is the PFS-4 rate based on RECIST 1.1. This is the proportion of subjects free of progression free at 4 months. The PFS-4 rate will be estimated using the binomial proportion along with the corresponding exact binomial 80% and 95% CIs. The PFS-4 rate will be tested using a null hypothesis that PFS-4 rate is $\leq 25\%$ tested against the alternative hypothesis of a PFS-4 rate $\geq 50\%$, using the 1-sample exact test of a single proportion, at the 1-sided 0.1 level. This analysis will be performed on the lenvatinib-naïve subjects in Full Analysis Set and Per Protocol Analysis Set, while subjects enrolled from Cohorts 1 and 2B will be summarized only as appropriate.

The PFS-4 rate will be analyzed using PFS-4 evaluable subjects. These are defined as follows.

PFS-4 evaluable subjects:

- includes subjects who were treated with study medication at least 18 weeks
- includes subjects who died or radiologically progressed within 18 weeks after the first administration of study medication. These subjects are not considered free of progression at 4 months.
- includes subjects who received anticancer treatment within 18 weeks after the first administration of study medication. These subjects are not considered free of progression at 4 months.
- excludes those who discontinue the study due to AE or other reasons than disease progression, death , or receiving anticancer treatment within 18 weeks after the first administration of study medication
- excludes subjects administered any study medication but had no baseline or no postbaseline tumor assessments.

SURGICALLY REMOVED LESIONS

For Cohorts 2B, 3A and 3B, removal of existing (not new) osteosarcoma metastatic lesion(s) is permitted after the completion of the first 4 months of the treatment period without PD. The time points for tumor response assessment after tumor removal will be considered ‘Not Evaluable’ unless the tumor response is considered PD for the following reasons:

- appearance of an unequivocal new lesion
- unequivocal progression of non-target lesions or target lesions

Lesions removed before the first 4 months are permitted only in the case of PD.

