13.2 Summary of Efficacy Analyses

Efficacy Variable	Analysis Set	Statistical Method	Tumor Assessments
PFS-4	Full Analysis Set, Per Protocol Analysis Set	Number (percent) of subjects who are alive, free of disease progression, and did not receive anticancer medication 4 months after the first dose, and its exact 80 and 95% CIs using method of Clopper and Pearson.	Investigator
		Cohort 2B: PFS-4 rate will be tested using a Null hypothesis that PFS-4 is $\leq 25\%$ tested against the alternative hypothesis of a PFS-4 $\geq 45\%$, using the 1-sample exact test of a single proportion, at the 1-sided 0.1 level.	
ORR	Full Analysis Set, Per Protocol Analysis Set	Cohort 3B: PFS-4 rate will be tested using a Null hypothesis that PFS-4 is $\leq 25\%$ tested against the alternative hypothesis of a PFS-4 $\geq 50\%$, using the 1-sample exact test of a single proportion, at the 1-sided 0.1 level.	Investigator
PFS	Full Analysis Set, Per Protocol Analysis Set	Number (percent) of subjects (with PR + CR) and its exact 95% CI using method of Clopper and Pearson.	Investigator
OS	Full Analysis Set	KM method: Median, Q1, and Q2 PFS will be presented, with 2-sided 95% CIs (Brookmeyer and Crowley). Cumulative probability of PFS at 4 and 12 months will be presented with 2-sided 80 and 95% CIs (Greenwood using the log-log). KM plot will also be provided.	Not Applicable

Efficacy Variable	Analysis Set	Statistical Method	Tumor Assessments	
		plot will also be provided.		
BOR	Full Analysis Set, Per Protocol Analysis Set	Number (percent) and 95% exact CIs will be provided for each BOR category	Investigator	
DOR	Full Analysis Set, Per Protocol Analysis Set	KM method: Median, Q1, and Q2 PFS will be presented, with 2-sided 95% CIs (Brookmeyer and Crowley).	Investigator	
TTP	Full Analysis Set, Per Protocol Analysis Set	Kaplan-Meier method: Median, Q1, and Q2 TTP will be presented with 2-sided 95% CIs (Brookmeyer and Crowley). Cumulative probability of TTP at 4 and 12 months will be presented with 2-sided 80 and 95% CIs (Greenwood using log-log). Kaplan-Meier plot will also be provided.	Investigator	

Efficacy Variable	Analysis Set	Statistical Method	Tumor Assessments
DCR	Full Analysis Set	Number (percent) of subjects (measurable disease with CR + PR + stable disease [SD] \geq 7 weeks, evaluable disease with CR + Non-CR/Non-PD \geq 7 weeks) and its exact 95% CI using method of Clopper and Pearson.	Investigator

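### PFS and TTP are censored at new anticancer therapy, which Protocol 9.4.8.2 judges as progression and PFS-4 counts as failure, with no reconciliation or sensitivity analysis

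*SAP*

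**What the plan says.** These places govern a subject who starts other anticancer therapy.

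- **Protocol 9.4.8.2**, on additional antitumor therapy while on study: "this will be judged to represent evidence of disease progression, and study medication will be discontinued". Section 9.4.8.3 lists what is permitted: limited palliative radiotherapy, and removal of existing osteosarcoma metastases under stated conditions.
- **Protocol 9.1.3**: after stopping treatment without progression, subjects are scanned for up to a year "for documented disease progression or until another anticancer therapy is initiated whichever occurs first".
- **SAP 5.4.2.1**, PFS-4 in Cohort 2B: the evaluable set "includes subjects who received anticancer treatment within 16 weeks after the first administration of study medication. These subjects are not considered free of progression". In Cohort 3B the set "includes subjects who received anticancer treatment within 18 weeks after the first administration of study medication" and again counts them as failures. Appendix 13.2 counts as successes only those "who are alive, free of disease progression, and did not receive anticancer medication 4 months after the first dose".
- **SAP 5.4.2.2**, row 6 of Table 3 (PFS) and Table 4 (TTP): the subject is censored at "Date of last adequate radiologic assessment prior to or on date of new anticancer treatment". The priority list under Table 3 applies this even when an event follows: "If a subject had new anticancer treatment before PD or death (No. 6), the subject will be censored". The list under Table 4 does the same for later progression.

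The Kaplan-Meier 4-month and 12-month PFS and TTP rates rest on these tables. They are to be reported with 80% and 95% intervals where enough subjects remain at risk. The SAP says its PFS censoring rules follow FDA 2007 endpoint guidance. Section 7 lists three changes (PFS-4 in Cohort 3A, analysis sets, growth plates and palatability) and does not mention row 6. No sensitivity analysis counts new therapy as an event.

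**The concern.** The same subject is a failure in the PFS-4 table and a censored observation in the PFS and TTP tables. Both tables give a 4-month rate with 80% and 95% intervals, so readers will set them side by side.

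Censoring is harmless only if it carries no information about the outcome. The protocol itself reads additional therapy as a sign of progression, so that assumption cannot be taken for granted here. Progression after the switch may also go unrecorded, because scheduled scanning after treatment ends stops when other therapy begins. If progression or death is recorded, row 6 still overrides it.

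What is at stake is the level of the secondary Kaplan-Meier PFS and TTP curves, their 4-month rates and their medians.

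**Working it through.** **The plan's own figure.** The documents give no expected number of subjects starting new therapy and no expected Kaplan-Meier rate. The nearest stated figure is the Cohort 2B design (SAP Section 4): at least 5 of 15, then at least 10 of 27, with p0 = 25%, p1 = 45%, one-sided alpha 0.1 and power 80%. With

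P(active | p) = Σ (x = 5 to 15) Bin(x; 15, p) × P[Bin(12, p) ≥ 10 − x],

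the result is 0.0973 at p = 0.25 and 0.8012 at p = 0.45. The design reproduces. PFS-4 already counts new therapy as failure, so row 6 does not touch it.

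**Size of the effect on the Kaplan-Meier rate.** Inputs from the documents: scans every 8 weeks (2B) or 6 weeks (3B); 1 month = 30.4375 days (SAP 8.3.2), so 4 months = 4 × 30.4375 = 121.75 days; 27 and 15 evaluable subjects. Assumed: the number k starting new therapy before 4 months, and the event pattern. There are no deaths in the pattern, so PFS and TTP coincide.

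Let s subjects be progression-free at 4 months, a progress at the first scan and b at the second, with k starting therapy between the two scans. Then N = s + a + b + k, and a is half of N − s − k, rounded up.

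- Therapy as an event: S(4 months) = s/N.
- Row 6, censored at the first scan: S(4 months) = (1 − a/N) × (1 − b/(N − a − k)).

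| Cohort | k | a, b | Event | Censored (row 6) | Rise, points |
|---|---|---|---|---|---|
| 2B, N = 27, s = 9 | 0 | 9, 9 | 33.3% | 33.3% | 0 |
| | 1 | 9, 8 | 33.3% | (18/27)(9/17) = 35.3% | 2.0 |
| | 2 | 8, 8 | 33.3% | (19/27)(9/17) = 37.3% | 3.9 |
| | 3 | 8, 7 | 33.3% | (19/27)(9/16) = 39.6% | 6.3 |
| | 5 | 7, 6 | 33.3% | (20/27)(9/15) = 44.4% | 11.1 |
| 3B, N = 15, s = 6 | 1 | 4, 4 | 40.0% | (11/15)(6/10) = 44.0% | 4.0 |
| | 2 | 4, 3 | 40.0% | (11/15)(6/9) = 48.9% | 8.9 |
| | 3 | 3, 3 | 40.0% | (12/15)(6/9) = 53.3% | 13.3 |

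**A second 3B pattern.** Take 15 subjects: 3 progress at Week 6, 2 at Week 12 and 1 at Week 18; 2 start therapy after a clean Week 6 scan; 7 stay progression-free. At Week 18 the rate is (12/15)(8/10)(7/8) = 56.0% censored, against 7/15 = 46.7% with therapy as an event. At day 121.75, with the Week 18 scan on day 126, it is (12/15)(8/10) = 64.0% against 8/15 = 53.3%. The gap is similar (9.3 and 10.7 points for two subjects), but the level depends on the day read.

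**Direction.** In 3,000 randomly generated data sets of 27, with one to six subjects starting therapy before 4 months, replacing the event by censoring on the same or an earlier day raised the 4-month rate every time. The smallest rise was 1.4 points.

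The reverse can occur when therapy starts after 4 months and the Week 16 scan was missed. Take 27 subjects: 8 progress at day 56, 8 at day 112, 2 start therapy at day 130, and 9 stay progression-free. Event coding gives 11/27 = 40.7%. Row 6 censors the two at day 56 and gives (19/27)(9/17) = 37.3%.

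**The case against.** The strongest case for the plan has four parts.

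1. The PFS censoring follows a declared convention, the FDA 2007 guidance. Preferring event coding as the main analysis is a choice between estimands, not the correction of an error.
2. Protocol 9.4.8.2 governs conduct on study and is tied to stopping study drug. It does not define an endpoint. Protocol 9.7.1.1 runs PFS and TTP to the first documentation of progression (or death, for PFS), the protocol sets no PFS censoring rules, and 9.7 leaves detail to the SAP. Whether 9.4.8.2 reaches therapy begun after study treatment has ended is unclear.
3. A reader might infer that the Kaplan-Meier 4-month rate and PFS-4 measure the same quantity and would agree if row 6 were changed. The documents do not support that. PFS-4 uses evaluable subjects, leaves out discontinuations for adverse events or other non-progression reasons, and uses 16 weeks (day 112) or 18 weeks (day 126). Kaplan-Meier PFS uses the Full Analysis and Per Protocol sets, censors such discontinuations (row 10), and reads 4 months at day 121.75.
4. Only secondary descriptive summaries change.

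All four limit the point. None explains, within the SAP, why secondary PFS treats these subjects differently from the primary endpoint. The PFS-4 rule carries no on-study limit, so the mismatch inside the SAP stands whatever the reach of 9.4.8.2. Whether Section 7 had to list row 6 as a change is arguable; that the SAP nowhere explains it is not.

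**Conclusion.** The mismatch is confirmed from the text. Where subjects start non-permitted therapy before 4 months, the Kaplan-Meier 4-month PFS and TTP rates will generally be higher than under the protocol's rule. The rise is about 2 points per subject in Cohort 2B and about 4 to 5 in Cohort 3B. These sizes rest on assumed event patterns and an assumed number of such subjects, and the effect is zero if there are none.

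A reader might go further and conclude that the PFS figures are inflated as a matter of fact, or that the primary result is compromised. The documents support neither. They give no count of such subjects, the direction can reverse in the missed-scan case, and the primary tests in 2B and 3B already count new therapy as failure.

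This is a cheap improvement to the reporting of secondary endpoints, not a fault in the primary analysis.

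**What to change.** - Prespecify an additional Kaplan-Meier analysis of PFS and TTP (4-month rate and median) that counts the start of non-permitted anticancer therapy as an event on its start date.
- Exclude the palliative radiotherapy and lesion removal permitted under Protocol 9.4.8.3 from that definition.
- State that in this analysis the new rule takes precedence over row 10 when therapy follows a discontinuation for reasons other than progression. Otherwise row 10 would censor the same subject.
- Report it beside the existing row 6 analysis.
- State in SAP 5.4.2.2 and Section 7 how row 6 differs from Protocol 9.4.8.2 and from PFS-4.

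The cost is a few lines of SAP text and one extra Kaplan-Meier run. The possible downside is a less favourable PFS figure next to the censored one.
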